## 7 Study Procedures

### 7.1 Schedule of Study Procedures

Tabular summaries of the assessments planned are presented in [Table 4](#) for subjects in the Q4 weeks arm and [Table 5](#) for subjects in the Q8 weeks arm. The dosing schedule for both arms (NGM621 and sham) is presented in [Table 6](#).

**Table 4. Q4 Week Arms Schedule of Assessments (NGM621 and Sham)***Study flowchart for Q4W Arms: Day 1, Week 1, Week 4 through Week 56*

Activity/ Assessment	Screen	Baseline	Treatment														Follow Up
	Day -28 to -3	Day 1	Wk 1	Wk 4	Wk 8	Wk 12	Wk 16	Wk 20	Wk 24	Wk 28	Wk 32	Wk 36	Wk 40	Wk 44	Wk 48	Wk 52 EOT 	Wk 56 EOS
Month				M1	M2	M3	M4	M5	M6	M7	M8	M9	M10	M11	M12	M13	M14
Visit Windows			$\pm 3$	$\pm 5$	$\pm 5$	$\pm 5$	$\pm 5$										
Informed Consent	X																
Inclusion/ Exclusion criteria	X																
Demographics	X																X
Ocular/Medical History	X																
Physical Exam	X																X
Body Weight	X																X
Pregnancy Testing 	X	X															X
Blood Sample (Hematology, chemistry) 	X																X
Urine Sample (Urinalysis, Drug Screen)	X																
Adverse Events	X	X	X	X	X	X	X	X	X	X	X	X	X	X	X	X	
Concomitant Medications	X	X	X	X	X	X	X	X	X	X	X	X	X	X	X	X	
Vital Signs	X									X							X
FRI Index 		X								X							X
NEI VFQ-25 		X								X							X
BCVA	OU	OU	OU	OU	OU	OU	OU	OU	OU	OU	OU	OU	OU	OU	OU	OU	OU
LLVA	OU									OU							OU
Reading Speed		X								X							X
Pre- and Post-dose IOP 	OU	OU	SE	SE	SE	OU	SE	SE	OU	SE	SE	OU	SE	SE	SE	OU	OU
Slit lamp Biomicroscopy	OU	OU	OU	OU	OU	OU	OU	OU	OU	OU	OU	OU	OU	OU	OU	OU	OU
Dilated Fundus Exam and Indirect Ophthalmoscopy	OU	OU	OU	OU	OU	OU	OU	OU	OU	OU	OU	OU	OU	OU	OU	OU	OU
SD-OCT 	OU						OU		OU		OU		OU		OU		OU

Activity/ Assessment	Screen	Baseline	Treatment														Follow Up	
	Day -28 to -3	Day 1	Wk 1	Wk 4	Wk 8	Wk 12	Wk 16	Wk 20	Wk 24	Wk 28	Wk 32	Wk 36	Wk 40	Wk 44	Wk 48	Wk 52 EOT 	Wk 56 EOS	
Month					M1	M2	M3	M4	M5	M6	M7	M8	M9	M10	M11	M12	M13	M14
Visit Windows			$\pm 3$	$\pm 5$	$\pm 5$	$\pm 5$	$\pm 5$	$\pm 5$	$\pm 5$	$\pm 5$	$\pm 5$	$\pm 5$	$\pm 5$	$\pm 5$	$\pm 5$	$\pm 5$	$\pm 5$	
Fundus Autofluorescence (FAF) 	OU									OU							OU	
Fluorescein angiography (FA) 	OU																	
Color Fundus Photography (CFP)	OU																OU	
Microperimetry at select sites (Study eye only) 	SE	SE								SE							SE	
Serum PK 		X	X	X			X		X				X		X	X	X	
Serum ADA 		X		X			X		X				X		X	X	X	
Serum NAb 		X		X			X		X				X		X	X	X	
Serum – C3 and CH50		X	X	X					X							X	X	
CCI																		
Randomization			X															
CCI																		
Dosing (Please see Table 6)																		

OU = both eyes; SE = study eye; X = Required.

 Females of childbearing potential only; Serum pregnancy test to be conducted at screening. Urine pregnancy test to be conducted on Day 1 and Week 52 visit. If pregnancy is suspected, a serum pregnancy test may be conducted.

 For the screening visit only, it is allowable to draw blood in the order of assessments as listed in the table OR the blood draw can occur right before the FA assessment to allow for a single needle stick.

 The patient-reported outcome (PRO) measures (NEI VFQ-25 and FRI Index) will be administered by the masked site staff (except for the VA examiner) prior to any other visit assessments being performed.

 Reference [Section 7.3.12.1](#) and the pharmacy manual for details.

 A FA and SD-OCT should be performed if the development of CNV is suspected in study eye. The central reading center must confirm this finding before any intervention is initiated. See [Section 7.3.15](#) for details.

 After randomization, if a patient misses a study visit when FAF images were scheduled to be taken, the images should be taken at the next scheduled visit.

 Microperimetry is optional and applies to select sites.

 PK, Anti-drug antibody and neutralizing antibody samples will be collected at Day 1 pre-dose, Week 1 post-dose (PK collection only), Weeks 4, 16, 24, 44, 48 pre-dose, and Weeks 52 and 56.

 For subjects who discontinue early from the study, the EOT visit assessments should be performed after a minimum of 28 days has elapsed from the last administered dose. See [Section 6.7](#) for details.

 For subjects who consented to the optional sample collection.

**Table 5. Q8 Week Arms Schedule of Assessments (NGM621 and Sham)**

*Study flowchart for Q8W Arms: Day 1, Week 1, Week 4 through Week 56*

Activity/Assessment	Screen	Baseline	Treatment															Follow Up
	Day -28 to -3	Day 1	Wk 1	Wk 4	Wk 8	Wk 12	Wk 16	Wk 20	Wk 24	Wk 28	Wk 32	Wk 36	Wk 40	Wk 44	Wk 48	Wk 52 EOT 	Wk56 EOS	
Month				M1	M2		M4		M6		M8		M10		M12	M13	M14	
Visit Windows			±3	±5	±5	±5	±5	±5	±5	±5	±5	±5	±5	±5	±5	±5	±5	
Informed Consent	X																	
Inclusion/Exclusion criteria	X																	
Demographics	X																X	
Ocular/Medical History	X																	
Physical Exam	X																X	
Body Weight	X																X	
Pregnancy Testing 	X	X															X	
Blood Sample (Hematology, chemistry) 	X																X	
Urine Sample (Urinalysis, Drug Screen)	X																	
Adverse Events 	X	X	X	X	X	X	X	X	X	X	X	X	X	X	X	X	X	
Concomitant Medications	X	X	X	X	X	X	X	X	X	X	X	X	X	X	X	X	X	
Vital Signs	X									X							X	
FRI Index 		X								X							X	
NEI VFQ-25 		X								X							X	

Activity/Assessment	Screen	Baseline	Treatment														Follow Up
	Day -28 to -3	Day 1	Wk 1	Wk 4	Wk 8	Wk 12	Wk 16	Wk 20	Wk 24	Wk 28	Wk 32	Wk 36	Wk 40	Wk 44	Wk 48	Wk 52 EOT 	Wk56 EOS
Month				M1	M2		M4		M6		M8		M10		M12	M13	M14
Visit Windows			$\pm 3$	$\pm 5$	$\pm 5$	$\pm 5$	$\pm 5$	$\pm 5$	$\pm 5$	$\pm 5$	$\pm 5$	$\pm 5$	$\pm 5$	$\pm 5$	$\pm 5$	$\pm 5$	
BCVA	OU	OU	OU	OU	OU		OU		OU		OU		OU		OU	OU	OU
LLVA	OU								OU							OU	
Reading Speed		X							X							X	
Pre- and Post-dose IOP 	OU	OU	SE		SE		SE		OU		SE		SE		SE	OU	OU
Slit lamp Biomicroscopy	OU	OU	OU	OU	OU		OU		OU		OU		OU		OU	OU	OU
Dilated Fundus Exam and Indirect Ophthalmoscopy	OU	OU	OU	OU	OU		OU		OU		OU		OU		OU	OU	OU
SD-OCT 	OU					OU		OU		OU		OU		OU		OU	OU
Fundus Autofluorescence (FAF) 	OU								OU							OU	
Fluorescein angiography (FA) 	OU																
Color Fundus Photography (CFP)	OU															OU	
Microperimetry at select sites (Study eye only) 	SE	SE							SE							SE	
Serum PK 		X	X	X	X		X		X				X		X	X	X
Serum ADA 		X		X	X		X		X				X		X	X	X
Serum NAb 		X		X	X		X		X				X		X	X	X
Serum – C3 and CH50		X	X	X					X								X
CCI																	
Randomization			X														
CCI																	
Dosing (please see Table 5)																	

OU = both eyes; SE = study eye; X= Required

 Females of childbearing potential only; Serum pregnancy test to be conducted at screening. Urine pregnancy test to be conducted on Day 1 and Week 52 visit. If pregnancy is suspected, a serum pregnancy test may be conducted.

 For the screening visit only, it is allowable to draw blood in the order of assessments as listed in the table OR the blood draw can occur right before the FA assessment to allow for a single needle stick.

 Columns shaded gray indicate that adverse event reporting will be by telephone (📞) for non-visit months (Weeks 12, 20, 28, 36, and 44) for subjects in the Q8W arm only.

 The patient-reported outcome (PRO) measures (NEI VFQ-25 and FRI Index) will be administered by the masked site staff (except for the VA examiner) prior to any other visit assessments being performed.

 Reference [Section 7.3.12.1](#) and the pharmacy manual for details.

 A FA and SD-OCT should be performed if the development of CNV is suspected in study eye. The central reading center must confirm this finding before any intervention is initiated. See [Section 7.3.15](#) for details.

 After randomization, if a patient misses a study visit when FAF images were scheduled to be taken, the images should be taken at the next scheduled visit.

 Microperimetry is optional and applies to select sites.

 PK, anti-drug antibody and neutralizing antibody samples will be collected at Day 1 pre-dose, at Week 1 post-dose (PK collection only), Week 4 post-dose, Weeks 8, 16, 24, 40, 48 pre-dose, and on Weeks 52 and 56.

 For subjects who discontinue early from the study, the EOT visit assessments should be performed after a minimum of 28 days has elapsed from the last administered dose. See [Section 6.7](#) for details.

 For subjects who consented to the optional sample collection.

**Table 6. Dosing Treatment Arms (NGM621 and Sham)**

Treatment Arm	Screen	Baseline	Treatment														Follow Up
	Day -28 to -3	Day 1	Wk 1	Wk 4	Wk 8	Wk 12	Wk 16	Wk 20	Wk 24	Wk 28	Wk 32	Wk 36	Wk 40	Wk 44	Wk 48	Wk 52 EOT	Wk 56 EOS
NGM621 15 mg Q4W		X 		X 													
Sham Q4W		X 		X 													
NGM621 15 mg Q8W		X 			X 												
Sham Q8W		X 			X 												

 Refer to [Section 7.3.12.1](#) and the pharmacy manual for details on treatment administration and pre- and post-dose IOP monitoring, and if needed, IOP management instructions.

## 7.2 Study Visit Procedures

### 7.2.1 Screening (Day -28 to Day -3) Visit

The following procedures will be performed at Screening:

- Obtain informed consent
- Inclusion/exclusion criteria assessment
- Demographics
- Ocular and medical history
- Physical Exam
- Measure body weight
- Serum pregnancy test for female subjects of child-bearing potential
- Hematology, Chemistry
- Urinalysis
- Urine drug screen
- Collect adverse events and concomitant medications
- Measure vital signs (including temperature, respiratory rate, and seated blood pressure and pulse)
- BCVA on both eyes
- LLVA on both eyes
- Intraocular pressure on both eyes
- Slit lamp biomicroscopy on both eyes
- Dilated fundus exam and indirect ophthalmoscopy on both eyes
- SD-OCT on both eyes
- Fundus autofluorescence on both eyes

- Fluorescein angiography on both eyes
- Color fundus photography on both eyes
- Microperimetry (at selected sites) on study eye
- Schedule Day 1 visit

### **7.2.2 Baseline (Day 1) Treatment Visit**

The following procedures/assessments will be performed:

#### **PRE-DOSE**

- Urine pregnancy test for female subjects of child-bearing potential. If pregnancy is suspected, a serum pregnancy test may be conducted
- Adverse events and concomitant medications
- FRI Index
- NEI VFQ-25
- BCVA on both eyes
- Measure reading speed
- Intraocular pressure on both eyes (prior to dilating eyes)
- Slit lamp biomicroscopy on both eyes
- Dilated fundus exam and indirect ophthalmoscopy on both eyes
- Microperimetry (at selected sites) on study eye
- Serum sample for PK
- Serum samples for ADA and NAb
- Serum sample for C3 and CH50
- **CCI** [REDACTED]
- **CCI** [REDACTED]
- Randomize and dose all subjects (Q4W and Q8W), as randomized

## **POST-DOSE**

- Level of vision (including finger counting, hand motion, and light perception) within 15 minutes post-dose on both eyes
- IOP post-dose on both eyes
- Schedule the next study visit

### **7.2.3 Week 1 ( $\pm 3$ days) Visit**

The following procedures/assessments will be performed:

- Adverse events and concomitant medications
- BCVA on both eyes
- IOP on study eye (prior to dilating eyes)
- Slit lamp biomicroscopy on both eyes
- Dilated fundus exam and indirect ophthalmoscopy on both eyes
- Serum sample for PK
- Serum sample for C3 and CH50.
- **CCI** [REDACTED]
- **CCI** [REDACTED]
- Schedule the next study visit

### **7.2.4 Week 4 ( $\pm 5$ days) Treatment Visit**

The following procedures/assessments will be performed:

## **PRE-DOSE**

- Adverse events and concomitant medications
- BCVA on both eyes
- IOP on study eye (prior to dilating eyes)
- Slit lamp biomicroscopy on both eyes

- Dilated fundus exam and indirect ophthalmoscopy on both eyes
- Serum sample for PK
- Serum samples for ADA and NAb
- Serum sample for C3 and CH50
- CCI [REDACTED]
- CCI [REDACTED]
- Dose Q4W subjects ONLY, as randomized

#### **POST-DOSE (Only Q4W arms)**

- Level of vision (including finger counting, hand motion, and light perception) within 15 minutes post-dose on study eye
- IOP on study eye
- Schedule the next study visit

#### **7.2.5 Week 8 ( $\pm$ 5 days) Treatment Visit**

The following procedures/assessments will be performed:

#### **PRE-DOSE**

- Adverse events and concomitant medications
- BCVA on both eyes
- IOP on study eye (prior to dilating eyes)
- Slit lamp biomicroscopy on both eyes
- Dilated fundus exam and indirect ophthalmoscopy on both eyes
- Serum sample for PK (Q8W arms only)
- Serum samples for ADA and NAb (Q8W arms only)
- Dose all subjects (Q4W and Q8W), as randomized

**POST-DOSE**

- Level of vision (including finger counting, hand motion, and light perception) within 15 minutes post dose on study eye
- IOP post-dose on study eye
- Schedule the next study visit

**7.2.6 Week 12 ( $\pm$  5 days) Treatment Visit (Q4W Arms ONLY)**

The following procedures/assessments will be performed:

**PRE-DOSE**

- Adverse events and concomitant medications
- BCVA on both eyes
- IOP on both eyes (prior to dilating eyes)
- Slit lamp biomicroscopy on both eyes
- Dilated fundus exam and indirect ophthalmoscopy on both eyes
- Dose Q4W subjects ONLY, as randomized

**POST-DOSE**

- Level of vision (including finger counting, hand motion, and light perception) within 15 minutes post dose on both eyes
- IOP post-dose on both eyes.
- Schedule the next study visit

**7.2.6.1 Week 12 ( $\pm$  5 days) Telephone Safety Visit (Q8W Arms ONLY)**

- The sites will contact subjects in the Q8W treatment arm via a telephone call to record adverse events and concomitant medications.

**7.2.7 Week 16 ( $\pm$  5 days) Treatment Visit**

The following procedures/assessments will be performed:

**PRE-DOSE**

- Adverse events and concomitant medications.
- BCVA on both eyes
- IOP on study eye (prior to dilating eyes)
- Slit lamp biomicroscopy on both eyes
- Dilated fundus exam and indirect ophthalmoscopy on both eyes
- SD-OCT on both eyes
- Serum sample for PK
- Serum samples for ADA and NAb
- Dose all subjects (Q4W and Q8W), as randomized.

**POST-DOSE**

- Level of vision (including finger counting, hand motion, and light perception) within 15 minutes post-dose on study eye
- IOP post dose on study eye
- Schedule the next study visit

**7.2.8 Week 20 ( $\pm$  5 days) Treatment Visit (Q4W Arms ONLY)**

The following procedures/assessments will be performed:

**PRE-DOSE**

- Adverse events and concomitant medications
- BCVA on both eyes
- IOP on study eye (prior to dilating eyes)
- Slit lamp biomicroscopy on both eyes

- Dilated fundus exam and indirect ophthalmoscopy on both eyes
- Dose Q4W subjects ONLY, as randomized

### **POST-DOSE**

- Level of vision (including finger counting, hand motion, and light perception) within 15 minutes post dose on study eye
- IOP post-dose on study eye
- Schedule the next study visit

#### **7.2.8.1 Week 20 ( $\pm$ 5 days) Telephone Safety Visit (Q8W Arms ONLY)**

- The sites will contact subjects in the Q8W treatment arm via a telephone call to record adverse events and concomitant medications.

#### **7.2.9 Week 24 ( $\pm$ 5 days) Treatment Visit**

The following procedures/assessments will be performed:

### **PRE-DOSE**

- Adverse events and concomitant medications
- Vital signs (including temperature, respiratory rate, and seated blood pressure and pulse)
- FRI Index
- NEI VFQ-25
- BCVA on both eyes
- LLVA on both eyes
- Reading speed
- IOP on both eyes (prior to dilating eyes)
- Slit lamp biomicroscopy on both eyes
- Dilated fundus exam and indirect ophthalmoscopy on both eyes
- SD-OCT on both eyes

- Fundus autofluorescence on both eyes
- Microperimetry (at selected sites) on study eye
- Serum sample for PK
- Serum samples for ADA and NAb
- Serum sample for C3 and CH50
- CCI [REDACTED]
- CCI [REDACTED]
- Dose all subjects (Q4W and Q8W), as randomized

## **POST-DOSE**

- Level of vision (including finger counting, hand motion, and light perception) within 15 minutes post-dose on both eyes
- IOP post-dose on both eyes
- Schedule the next study visit

### **7.2.10 Week 28 ( $\pm$ 5 days) Treatment Visit (Q4W Arms ONLY)**

The following procedures/assessments will be performed:

## **PRE-DOSE**

- Adverse events and concomitant medications.
- BCVA on both eyes
- IOP on study eye (prior to dilating eyes)
- Slit lamp biomicroscopy on both eyes
- Dilated fundus exam and indirect ophthalmoscopy on both eyes
- Dose Q4W subjects ONLY, as randomized

**POST DOSE**

- Level of vision (including finger counting, hand motion, and light perception) within 15 minutes post dose on study eye
- IOP post-dose on study eye
- Schedule the next study visit

**7.2.10.1 Week 28 ( $\pm$  5 days) Telephone Safety Visit (Q8W Arms ONLY)**

- The sites will contact subjects in the Q8W treatment arm via a telephone call to record adverse events and concomitant medications.

**7.2.11 Week 32 ( $\pm$  5 days) Treatment Visit**

The following procedures/assessments will be performed:

**PRE-DOSE**

- Adverse events and concomitant medications
- BCVA on both eyes
- IOP on study eye (prior to dilating eyes)
- Slit lamp biomicroscopy on both eyes
- Dilated fundus exam and indirect ophthalmoscopy on both eyes
- SD-OCT on both eyes
- Dose all subjects (Q4W and Q8W), as randomized

**POST-DOSE**

- Level of vision (including finger counting, hand motion, and light perception) within 15 minutes post dose on study eye
- IOP post-dose on study eye
- Schedule the next study visit

**7.2.12 Week 36 ( $\pm$  5 days) Treatment Visit (Q4W Arms ONLY)**

The following procedures/assessments will be performed:

**PRE-DOSE**

- Adverse events and concomitant medications
- BCVA on both eyes
- IOP on both eyes (prior to dilating eyes)
- Slit lamp biomicroscopy on both eyes
- Dilated fundus exam and indirect ophthalmoscopy on both eyes

**POST-DOSE**

- Level of vision (including finger counting, hand motion, and light perception) within 15 minutes post-dose on both eyes
- IOP post-dose on both eyes
- Schedule the next study visit

**7.2.12.1 Week 36 ( $\pm$  5 days) Telephone Safety Visit (Q8W Arms ONLY)**

- The sites will contact subjects in the Q8W treatment arm via a telephone call to record adverse events and concomitant medications.

**7.2.13 Week 40 ( $\pm$  5 days) Treatment Visit**

The following procedures/assessments will be performed:

**PRE-DOSE**

- Adverse events and concomitant medications
- BCVA on both eyes
- IOP on study eye (prior to dilating eyes)
- Slit lamp biomicroscopy on both eyes
- Dilated fundus exam and indirect ophthalmoscopy on both eyes
- SD-OCT on both eyes

- Serum sample for PK
- Serum samples for ADA and NAb
- Dose Q4W & Q8W subjects, as randomized

### **POST-DOSE**

- Level of vision (including finger counting, hand motion, and light perception) within 15 minutes post dose on study eye
- IOP post dose on study eye
- Schedule the next study visit

#### **7.2.14 Week 44 ( $\pm$ 5 days) Treatment Visit (Q4W Arms ONLY)**

The following procedures/assessments will be performed:

### **PRE-DOSE**

- Adverse events and concomitant medications
- BCVA on both eyes
- IOP on study eye (prior to dilating eyes)
- Slit lamp biomicroscopy on both eyes
- Dilated fundus exam and indirect ophthalmoscopy on both eyes
- Dose Q4W subjects ONLY, as randomized

### **POST-DOSE**

- Level of vision (including finger counting, hand motion, and light perception) within 15 minutes post-dose on study eye
- IOP post-dose on study eye
- Schedule the next study visit

#### **7.2.14.1 Week 44 ( $\pm$ 5 days) Telephone Safety Visit (Q8W Arms ONLY)**

- The sites will contact subjects in the Q8W treatment arm via a telephone call to record adverse events and concomitant medications.

**7.2.15 Week 48 ( $\pm$  5 days) Treatment Visit**

The following procedures/assessments will be performed at Week 48:

**PRE-DOSE**

- Adverse events and concomitant medications
- BCVA on both eyes
- IOP on study eye (prior to dilating eye)
- Slit lamp biomicroscopy on both eyes
- Dilated fundus exam and indirect ophthalmoscopy on both eyes
- Serum sample for PK
- Serum samples for ADA and NAb
- Dose Q4W & Q8W subjects, as randomized

**POST-DOSE**

- Level of vision (including finger counting, hand motion, and light perception) within 15 minutes post-dose on study eye
- IOP post-dose on study eye
- Schedule the next study visit

**7.2.16 Week 52 ( $\pm$  5 days) – End of Treatment (EOT) Visit (also Early Termination visit for any subjects that discontinue before week 52)**

The following procedures/assessments will be performed:

- Demographics
- Physical exam
- Measure body weight
- Urine pregnancy test for female subjects of child-bearing potential. If pregnancy is suspected, a serum pregnancy test may be conducted.
- Hematology, Chemistry

- Adverse events and concomitant medications
- Measure vital signs (including temperature, respiratory rate, and seated blood pressure and pulse)
- FRI Index
- NEI VFQ-25
- BCVA on both eyes
- LLVA on both eyes
- Reading speed
- IOP on both eyes (prior to dilating eyes)
- Slit lamp biomicroscopy on both eyes
- Dilated fundus exam and indirect ophthalmoscopy on both eyes
- SD-OCT on both eyes
- Fundus autofluorescence on both eyes
- Color fundus photography on both eyes
- Microperimetry (at selected sites) on study eye
- Serum sample for PK
- Serum samples for ADA and NAb
- Serum sample for C3 and CH50
- CCI [REDACTED]
- CCI [REDACTED]

#### **7.2.17            Week 56 ( $\pm$ 5 days) – Follow up and End of Study Visit**

The following procedures/assessments will be performed:

- Adverse events and concomitant medications

- Measure vital signs (including temperature, respiratory rate, and seated blood pressure and pulse)
- BCVA on both eyes
- IOP on both eyes (prior to dilating eyes)
- Slit lamp biomicroscopy on both eyes
- Dilated fundus exam and indirect ophthalmoscopy on both eyes
- SD-OCT on both eyes
- Serum sample for PK
- Serum samples for ADA and NAb
- If patient consented to the optional buccal swab and it was not collected at a prior visit, please collect the sample
- This visit marks the end of study participation for all subjects

### **7.3 Study Assessments and Evaluations**

#### **7.3.1 Demographic/ Ocular Characteristics**

Demographic characteristics including sex, age, race, and ethnicity and ocular characteristics such as eye/iris color will be recorded ([Table 4](#) and [Table 5](#)).

#### **7.3.2 Ocular/Medical and Surgical History**

The Investigator or designee will collect a complete ocular, medical, and surgical history ([Table 4](#) and [Table 5](#)). Smoking history will be collected.

#### **7.3.3 Body Weight**

Body weight will be collected as determined by the Schedule of Study Procedures ([Table 4](#) and [Table 5](#)).

#### **7.3.4 Vital Signs**

Vital signs assessments will include temperature (C°), respiratory rate (breaths per minute), systolic and diastolic blood pressure (mmHg) and pulse rate (bpm). Blood pressure and pulse rate will be measured after the subject has been resting quietly in a seated position for at least

5 minutes. Any clinically significant abnormal vital sign assessment requires at least one repeat measurement.

Vital signs abnormalities that (1) are considered clinically significant initially and on confirmation, (2) require a subject to be discontinued from the study, or (3) require a subject to receive treatment will be recorded as AEs.

### **7.3.5 Physical Examination**

A focused physical examination of specific body system(s) relating to any presenting problem or current concern(s) of the subject will be conducted. This may involve one or more body system. An eye exam including EOM movements will be performed, and abnormal findings will be carefully documented in the subject's eCRF. An abnormal physical examination finding that is considered clinically significant and requires the subject to be discontinued from the study or requires intervention will be recorded as an AE.

### **7.3.6 Clinical Laboratory Examinations**

At the scheduled visit, specimens should be collected prior to study eye treatment and FAF assessments (if applicable). The specimens will be forwarded to the central laboratory. The central laboratory will either perform the analysis or forward samples to Sponsor or its designee for analysis and/or storage.

The Laboratory Manual will contain the necessary instructions for obtaining, processing, storing and shipping of all samples. Clinical laboratory kits will be provided to sites by the central laboratory.

The following assessments will be performed as indicated:

- Hematology: hemoglobin, hematocrit, quantitative platelet count, red blood cell counts, white blood cell counts, and differentials, including neutrophils, bands, lymphocytes, basophils, eosinophils, and monocytes (absolute)
- Chemistry: sodium, potassium, chloride, bicarbonate, glucose, blood urea nitrogen, creatinine, calcium, phosphorus, total and direct bilirubin, total protein, albumin, aspartate aminotransferase, alanine aminotransferase, lactate dehydrogenase, alkaline phosphatase, and uric acid
- Urinalysis: pH, specific gravity, glucose, ketones, bilirubin, protein, urobilinogen and microscopic examination
- Initial serum pregnancy test ( $\beta$ -human chorionic gonadotropin) for women of childbearing potential, including those who have had tubal ligation. If positive, study treatment will not be administered.

- Urine pregnancy test prior to each study treatment for women of childbearing potential, including those who have had tubal ligation. If positive, perform the serum pregnancy test. If the serum pregnancy test is positive, do not administer the study treatment.
- Urine drug screen assessment
- Complement pathway assessment assay (C3 and CH50): In all subjects serum samples will be collected as outlined in [Table 4](#) and [Table 5](#).
- Systemic PK, ADA, and NAb Evaluation: Serum samples for PK, ADA, and NAb will be collected as outlined in [Table 4](#) and [Table 5](#). Processing, storage, and shipping instructions for these PK blood samples will be presented in the study Lab Manual.
- **CCI**  
[REDACTED]
- If the subject gave consent for any remaining blood (including plasma and serum) samples to be retained for optional research, then the samples may be stored for up to 15 years after the date of final closure of the associated clinical database.

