Optional Buccal Swab for genetic testing 		One-time collection at any visit from Day 1 to EOS. Collect only if subject has consented to optional procedure.															
Dosing (Please see Table 6 )																	

OU = both eyes; SE = study eye; X= Required

 Females of childbearing potential only; Serum pregnancy test to be conducted at screening. Urine pregnancy test to be conducted on Day 1 and Week 48 visit. If pregnancy is suspected, a serum pregnancy test may be conducted.

 For the screening visit only, it is allowable to draw blood in the order of assessments as listed in the table OR the blood draw can occur right before the FA assessment to allow for a single needle stick.

 The patient-reported outcome (PRO) measures (NEI VFQ-25 and FRI Index) will be administered by the masked site staff (except for the VA examiner) prior to any other visit assessments being performed.

 Reference [Section 7.3.12.1](#) and the pharmacy manual for details.

[5] A FA and SD-OCT should be performed if the development of CNV is suspected in study eye. The central reading center must confirm this finding before any intervention is initiated. See [Section 7.3.15](#) for details.

[6] After randomization, if a patient misses a study visit when FAF images were scheduled to be taken, the images should be taken at the next scheduled visit.

[7] Microperimetry is optional and applies to select sites.

[8] PK, Anti-drug antibody and neutralizing antibody samples will be collected at Day 1 pre-dose, Week 1 post-dose (PK collection only), Weeks 4, 16, 24, 44, 48 pre-dose, and on Weeks 52 and 56.

[9] For subjects who discontinue early from the study, the EOT visit assessments should be performed after a minimum of 28 days has elapsed from the last administered dose. See [Section 6.7](#) for details.

[10] For subjects who consented to the optional sample collection.

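### Section 7.3.6 requires a urine pregnancy test before every dose, but the schedules and visit lists prompt it at only one or two dosing visits

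*Combined protocol and SAP*

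**What the plan says.** Section 7.3.6 (Clinical Laboratory Examinations) asks for a "Urine pregnancy test prior to each study treatment for women of childbearing potential", and it includes women who have had a tubal ligation. A positive urine result leads to a serum test, and then: "If the serum pregnancy test is positive, do not administer the study treatment".

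The schedule says something else. Footnote 1 to Table 4 (Q4W) and to Table 5 (Q8W) reads "Urine pregnancy test to be conducted on Day 1 and Week 52 visit". Footnote 1 to each of the two synopsis schedules reads "Urine pregnancy test to be conducted on Day 1 and Week 48 visit". All four footnotes also allow a serum test if pregnancy is suspected.

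The Section 7.2 visit lists agree with Tables 4 and 5. The item "Urine pregnancy test for female subjects of child-bearing potential" appears before the dose on Day 1 (7.2.2) and again at the Week 52 End of Treatment visit (7.2.16), where no dose is given. No list from Week 4 to Week 48 contains it. Week 8 (7.2.5), for example, has "Dose all subjects (Q4W and Q8W), as randomized" and Week 48 (7.2.15) has "Dose Q4W & Q8W subjects, as randomized", each without a pregnancy test.

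**The concern.** The protocol gives three different timings for one test: before every dose, on Day 1 and at Week 52, or on Day 1 and at Week 48. The test matters because its result decides whether a dose is given. A coordinator who works from the schedule or the visit list for the day would dose an affected woman at most visits without the check that Section 7.3.6 requires, and each such dose would be a deviation from that section. The Week 52 test cannot serve the purpose, because no dose follows it.

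What is at stake is procedural safety in a small subgroup. The estimand, power, type I error and masking are not involved.

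**Working it through.** There is no stated figure to reproduce. The check compares the texts and counts the doses that have no scheduled test.

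**Dosing visits.** These come from the headings and dose lines in Section 7.2, because the columns of Table 6 cannot be read reliably in the available copy.
- Q4W arms: Day 1 plus Weeks 4, 8, 12, ..., 48 gives 1 + 12 = 13 doses.
- Q8W arms: Day 1 plus Weeks 8, 16, 24, 32, 40, 48 gives 1 + 6 = 7 doses.
- Week 36 needs a judgement. Its list (7.2.12) has no dose line, but the heading calls it a "Treatment Visit (Q4W Arms ONLY") visit and it has a post-dose section, so it is counted. Leaving it out gives 13 − 1 = 12 Q4W doses.

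**Doses with no scheduled urine test** = doses − scheduled tests that fall on a dosing visit.

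| Source | Scheduled tests | Tests on a dosing visit | Q4W without a test | Q8W without a test |
|---|---|---|---|---|
| Section 7.3.6 | every dose | all | 0 of 13 | 0 of 7 |
| Tables 4/5 and Section 7.2 | Day 1, Week 52 | 1 (Day 1) | 13 − 1 = 12 of 13 | 7 − 1 = 6 of 7 |
| Synopsis footnotes | Day 1, Week 48 | 2 | 13 − 2 = 11 of 13 | 7 − 2 = 5 of 7 |

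Without Week 36, the Q4W figures become 12 − 1 = 11 of 12 and 12 − 2 = 10 of 12. The Q8W figures do not change.

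**Does any text settle the conflict?** The list in Section 7.3.6 is introduced as assessments done where indicated, which might be read as deferring to the tables. But the urine-test item sets its own timing. The C3/CH50 item and the PK/ADA/NAb item in the same list refer expressly to Tables 4 and 5, and this one does not. The one precedence rule, at the start of Section 8, ranks the SAP over the protocol's statistical section and has no bearing here.

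**Is the synopsis a separate intention or a slip?** The Week 48 visit list has no pregnancy test and the Week 52 list does, so a slip for Week 52 is the likelier reading. That is an inference.

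**The case against.** The strongest reply is that the texts can all be obeyed together. No footnote says the test is done on those days alone. Section 7.3.6 is explicit, Section 9.1.3 binds investigators to the protocol, and Section 7.1 describes the tables as summaries. A site that tests before every dose and again at Week 52 complies with everything. This is right as far as it goes: the fault is a missing prompt, and compliance is not impossible. But the detailed visit lists omit the test as well as the tables, so a site following either would miss it. That sites tend to work from these lists is general experience; the documents do not say so.

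The second reply concerns weight. Subjects are at least 55, childbearing potential means under 2 years of amenorrhea, and documented postmenopausal women are classed as not of childbearing potential, so the group may be empty. A third of subjects (106 of 318) receive sham only, where a missed test involves no drug exposure. Serum exposure in Phase 1 was below the level that inhibits complement systemically, although this does not establish reproductive safety. Other safeguards also apply: negative tests before the first dose, contraception or abstinence to Week 56, a serum test on suspicion, possible discontinuation for pregnancy, and immediate reporting with follow-up to outcome. All of this stands and keeps the point minor. A test done on suspicion is still no substitute for the routine check.

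Third, the documents do not show which text was intended, and amending one item in Section 7.3.6 would be simpler than marking every dosing visit. That also stands, and either alignment would resolve the conflict.

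**Conclusion.** The concern holds. The protocol's rule for a test that can stop a dose does not match its schedule or its visit lists. An affected woman has no scheduled urine test at 12 of 13 Q4W doses or 6 of 7 Q8W doses under Tables 4 and 5 and Section 7.2, and at 11 of 13 or 5 of 7 under the synopsis footnotes. The Q4W figures assume a Week 36 dose.

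These are counts of doses for one affected woman and say nothing about how many such women there are. The documents give no number, and the entry criteria suggest very few or none. The point is an internal inconsistency in a safety procedure. It is worth correcting but is not a threat to the trial's conclusions.

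**What to change.** Take Section 7.3.6 as the rule. Mark a pre-dose urine test, for women of childbearing potential only, at every dosing visit in Tables 4 and 5, in both synopsis schedules and in the Section 7.2 lists. Keep the Week 52 test, and change Week 48 in the synopsis footnotes so that they match. An affected woman would then have 13 scheduled pre-dose tests (Q4W) or 7 (Q8W), where Tables 4 and 5 now schedule 1. That is 12 or 6 more scheduled tests, all of which Section 7.3.6 already demands.

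If testing before each dose is not intended, amend Section 7.3.6 to the Day 1 and Week 52 timing and correct the synopsis footnotes.

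Either way the cost is text and table alignment, of the kind this amendment already makes for IOP and for ADA/NAb sampling. The first option also brings a few urine tests in a very small subgroup. No analysis changes.
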